2.6.2.2 Adverse events of special interest (AESI) / grouping of AEs

An adverse event of special interest is a grouping of adverse events that are of scientific and medical concern specific to compounds PDR001 or NIR178. These groupings are defined using MedDRA terms, SMQs (standardized MedDRA queries), HGLTs (high level group terms), HLT (high level terms) and PTs (preferred terms). Customized SMQs (Novartis MedDRA queries, NMQ) may also be used. A NMQ is a customized group of search terms which defines a medical concept for which there is no official SMQ available or the available SMQ does not completely fit the need. It may include a combination of single terms and/or an existing SMQ, narrow or broad.

The reporting of AESIs will follow similar conventions as used for AEs (see General analysis conventions in [Section 2.1](#)).

Given that only PDR001 specific electronic Case Retrieval Strategy (eCRS) exists, summaries of AESI associated with the combination (NIR178 + PDR001) will be reported using PDR001 specific eCRS for the combination arm by treatment groups. For each specified AESI, number (%) of patients with at least one event of the AESI occurring during on-treatment period will be summarized together with the individual preferred terms in that grouping. In addition, number (%) of patients with at least one AESIs by maximum CTC grade will be summarized.

A listing of all grouping levels down to the MedDRA preferred terms, based on the eCRS used to define each AESI, will be generated.

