6.2.2 Follow-up for toxicities

The emergence of Immune-Related AE (irAE) may be anticipated based on the mechanism of action of immunomodulatory therapies.

An irAE is any clinically significant adverse event affecting any organ that is associated with study drug exposure, is consistent with an immune-mediated mechanism, and where alternative explanations have been investigated and ruled out or are considered to be unlikely. Serologic, histologic (tumor sample) and immunological assessments should be performed as deemed appropriate by the Investigator to verify the immune-related nature of the AE. An empiric trial of corticosteroids may also contribute to understanding the etiology of a potential irAE.

Consensus management algorithms for irAEs have been developed and are available to assist investigators in assessing and managing irAEs (refer to [Section 6.2.1](#) Dose modifications).

Patients whose treatment is interrupted or permanently discontinued due to an irAE, AE or clinically significant laboratory value, must be followed-up at least once a week (or more frequently if required by institutional practices, or if clinically indicated) for 4 weeks, and subsequently at approximately 4-week intervals, until resolution or stabilization of the event, whichever comes first.

All patients must be followed up for irAEs, AEs and SAEs for up to 150 days following the last dose of PDR001 or up to 30 days following the last dose of NIR178.

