10.5.2.2 Adverse events (AEs)

Summary tables for adverse events (AEs) will include only AEs that started or worsened during the on-treatment period, the **treatment-emergent** AEs. Additional select summaries will be produced using all related AEs that started or worsened during the combined on-treatment and post-treatment periods.

The incidence of treatment-emergent adverse events (new or worsening from baseline) will be summarized by system organ class and or preferred term, severity (based on CTCAE grades), type of adverse event, relation to study treatment by tumor type and treatment group.

Serious adverse events, non-serious adverse events and adverse events of special interest (AESI) during the on-treatment period will be tabulated.

All deaths (on-treatment and post-treatment) will be summarized.

All AEs, deaths and serious adverse events (including those from the pre and post-treatment periods) will be listed and those collected during the pre-treatment and post-treatment period will be flagged.

All safety data from the patients from Japanese safety run-in part will be summarized separately. More details will be provided in the SAP.

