2.1.1.2 Date of first/last administration of a study drug and study treatment

The date of first (last) administration of a study drug is defined as the first (last) date when a non-zero dose of a drug is administered and recorded on the treatment page eCRF. The date of first/last administration of study drug will also be referred as start/end date of study drug.

The date of first (last) administration of study treatment is derived as the first (last) date when a non-zero dose of either component of the treatment (NIR178 or PDR001) was administered and recorded on the DAR eCRF.

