2.1.1.5 On-treatment assessment/event and observation periods

The overall observation period will be divided into three mutually exclusive segments:

pre-treatment period: from day of patient’s first informed consent to the day before first administration of study treatment

on-treatment period: from date of first administration of study treatment to 30 days after date of last actual administration of study treatment (including start and stop date). This period constitutes ***safety follow-up*** on all patients for 30 days after the last administration of study treatment.

post-treatment period: starting at day 31 after the last administration of study treatment. This period will constitute the following follow-up periods:

- ***extended safety follow-up period:*** all patients receiving PDR001 will continue to have safety evaluations for 150 days after the last dose of PDR001 or 30 days after the last dose of NIR178, whichever occurs later.
- ***disease progression follow-up period:*** Patients who discontinue study treatment for any reason other than death, disease progression per confirmed iRECIST or per Cheson (for DLBCL) or per PCWG3 guidance (for mCRPC) while on treatment, clinical deterioration or clinical progression, lost to follow-up, consent withdrawal or study termination, will have tumor evaluation assessments every 8 weeks (+/- 7 days) during the first 40 weeks,

and every 12 weeks (+/- 7 days) thereafter until disease progression, death, loss to follow-up or withdrawal of consent, whichever occurs first.

- **survival follow-up period:** Upon completion of the 150-day safety follow-up or disease progression follow-up, all patients (except for those in Japanese safety run in) will be followed for survival every 12 weeks until any of the following events (whichever occurs first): death, withdrawal of consent, loss to follow-up or at least 24 months from the first dose of study treatment.

Patients enrolled to another clinical study or alternate treatment (Protocol Section 4.3) will not have follow-up for safety, disease progression and survival assessments performed.

If dates are incomplete in a way that clear assignment to pre-, on-, post-treatment period cannot be made, then the respective data will be assigned to the on-treatment period.

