2.6.2 Safety objectives

All safety analyses will be based on the safety set (see [Section 2.2.2](#)), which will be used for presenting summaries and listings by treatment groups and overall patients following the general analysis conventions defined under [Section 2.1](#).

The assessment of safety is based on the type and frequency of AEs as well as on the number of laboratory values that fall outside of pre-determined ranges (CTCAE grading limits or normal ranges as appropriate). Other safety data include electrocardiogram and vital signs.

All safety reporting will be based on observation periods defined in [Section 2.1.1.5](#).

Safety summaries (tables, figures) will primarily be based on all data from the on-treatment period with the exception of baseline data which will also be summarized where appropriate (e.g. change from baseline summaries). In addition, a separate summary for death including on treatment and post treatment deaths will be provided. Following the last administration of study treatment, adverse events (including serious adverse events), and new antineoplastic therapies will be collected for a period of 150 days. Following start of new antineoplastic therapy only treatment related adverse events will be collected. Select summaries of related adverse events will be produced for the combined on-treatment and post-treatment periods (see Protocol Section 10.5.2.2).

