All AEs collected on the AE eCRF page will be listed with the information collected on those AEs e.g. AE relationship to study drug, AE outcome, etc. AEs with start date in the post-treatment period will be flagged in the listings; those that start in the pre-treatment period will be identified by study day prefixed with a ‘-‘ (a negative sign). Additionally, listings for AEs and SAEs on screened patients who are not treated will be provided with information on those AEs including start-end dates, outcome etc.

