2.6.2.4 EudraCT and clinicaltrials.gov requirements for AEs and Death summaries

For the legal requirements of clinicaltrials.gov and EudraCT, two tables (listed below) must be produced for treatment-emergent safety events (AEs/SAEs and deaths) that occurred for **150 days** after the last dose of PDR001 or 30 days after the last dose of NIR178, whichever occurred later.

1. Deaths and serious adverse events, by system organ class and preferred term.
2. Non-serious AEs regardless of study drug relationship, with an incidence rate greater than 5% by SOC and PT.

These summaries will include any events starting or worsening in the on-treatment period.

If for the same patient, several consecutive AEs (irrespective of study treatment causality, seriousness, and severity) occurred with the same SOC and PT:

- a single occurrence will be counted if there is ≤ 1 day gap between the end date of the preceding AE and the start date of the consecutive AE;
- more than one occurrence will be counted if there is > 1 day gap between the end date of the preceding AE and the start date of the consecutive AE.

The presence of at least one SAE / SAE suspected to be study drug related / non SAE has to be checked in a block e.g., among AEs in a ≤ 1 day gap block, if at least one SAE is occurring, then one occurrence is calculated for that SAE.

At the time of xml preparation, a single file per registry (i.e., 1 file for EudraCT and 1 file for CT.gov). with all reporting groups in the study will need to be submitted to the CDO.

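### AESI tables close 30 days after the later last dose, although immune-related events are collected to 150 days after PDR001 and no AESI-grouped table covers the remainder

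*SAP*

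**What the plan says.** **AESI tables.** SAP 2.6.2.2 builds the AESI groups for the combination from the PDR001-specific case retrieval strategy. For each group, the "number (%) of patients with at least one event of the AESI occurring during on-treatment period will be summarized". A second table gives patients by maximum CTC grade. It names no period, so it takes the default in SAP 2.6.2, which bases safety tables primarily on the on-treatment period. Protocol 10.5.2.2 agrees: "adverse events of special interest (AESI) during the on-treatment period will be tabulated".

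**End of the on-treatment period.** SAP 2.1.1.5 closes it 30 days after the last administration of study treatment. SAP 2.1.1.2 defines first and last administration as "the first (last) date when a non-zero dose of either component of the treatment (NIR178 or PDR001) was administered", so the drug stopped later sets the end.

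**Collection.** Protocol 6.2.2 requires more: "All patients must be followed up for irAEs, AEs and SAEs for up to 150 days following the last dose of PDR001". SAP 2.1.1.5 places this extended follow-up in the post-treatment period: "all patients receiving PDR001 will continue to have safety evaluations for 150 days after the last dose of PDR001", or for 30 days after NIR178 if that is later.

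**Later events.** SAP 2.6.2.1 lists them: "AEs with start date in the post-treatment period will be flagged in the listings". SAP 2.6.2 promises some summaries of related events over both periods, without naming them. SAP 2.6.2.3 summarises post-treatment deaths. SAP 2.6.2.4 sets up two registry tables by system organ class and preferred term with a 150-day window.

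**The concern.** Safety is a secondary objective, and Protocol 2.6 warns that the combination may raise the incidence of immune-related events. The AESI tables are where a reader would look for that signal. Their groups are defined by PDR001, and the 150-day follow-up is also tied to PDR001, yet the tables stop well before that follow-up ends for ordinary stopping patterns.

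A patient whose first AESI starts after the cut-off appears in the incidence table as having had none. A patient whose AESI worsens after it appears at the lower grade. Because the window runs from the later of the two last doses, the time covered after PDR001 also depends on the NIR178 schedule, and SAP 1.1.2 compares safety across the Part 2 schedules.

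**Working it through.** **Inputs**
- On-treatment end: later last dose + 30 days (SAP 2.1.1.2 and 2.1.1.5).
- Collection end: last PDR001 dose + 150 days (Protocol 6.2.2, SAP 2.1.1.5).
- Dosing in a 28-day cycle (Protocol 6.1.1): PDR001 on day 1; NIR178 on days 1–28 (S1), 1–14 (S2), or 1–7 and 15–21 (S3).
- Patients treated in Part 2: 22, 20 and 20; treated in all by 3 August 2020: 266, including 6 in the Japanese run-in (Protocol, Amendment 06, Study Status).

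**Formula.** Let L be the days from the last PDR001 dose to the last dose of either drug. AESI tables then cover 30 + L days after PDR001, and the uncovered part of the 150 days is max(0, 150 − (30 + L)) = max(0, 120 − L).

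| Stopping pattern | L | Covered after PDR001 | Not covered | Share of 150 days |
|---|---|---|---|---|
| Both drugs stop the same day | 0 | 30 | 120 | 80.0% |
| S2, last cycle completed (day 14) | 13 | 43 | 107 | 71.3% |
| S3, last cycle completed (day 21) | 20 | 50 | 100 | 66.7% |
| S1, last cycle completed (day 28) | 27 | 57 | 93 | 62.0% |
| NIR178 alone for 120 days or more after PDR001 | ≥120 | ≥150 | 0 | 0% |

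With completed last cycles, covered time differs between schedules by up to 57 − 43 = 14 days.

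**Effect of one omitted patient.** In a Part 2 schedule: 1/22 = 4.5 or 1/20 = 5.0 percentage points. Over all treated patients: 1/266 = 0.4 points, and the same to one decimal without the run-in (1/260).

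**Does another specified output fill the gap?**
- *Summaries of related events over both periods*: not itemised, limited to related events, not described by AESI group, and absent from the list of AE tables in SAP 2.6.2.1.
- *Registry tables*: by organ class and preferred term, with non-serious terms shown only above 5% incidence. One patient in 20 is exactly 5.0% and would not qualify. The window is also unclear, because after citing 150 days the section adds: "These summaries will include any events starting or worsening in the on-treatment period".
- *Death summaries*: fatal events only.
- *AESI listing in SAP 2.6.2.2*: shows how each group maps to preferred terms; it does not report late events.
- *Flagged AE listings*: contain the data, but ungrouped.

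Patient counts by AESI group cannot be recovered from preferred-term tables, because one patient may contribute several terms to the same group.

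**The case against.** The on-treatment window is a deliberate choice, stated consistently in both documents, and nothing about the AESI tables is undefined. An immune-related event as Protocol 6.2.2 defines it would normally be judged related, so it should enter the promised combined-period summaries. The output shells are a separate document (SAP 1) and might include an AESI-grouped table.

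Late ascertainment is also weaker. SAP 2.6.2 says "Following start of new antineoplastic therapy only treatment related adverse events will be collected". Follow-up at 30, 90 and 150 days may be by telephone (Protocol 7.1.5), and patients who transfer to another study have no safety follow-up (Protocol 7.1.5.1). Finally, the Part 2 schedule was chosen before this SAP version (Protocol 2.2), and the study closed for insufficient efficacy (SAP 4), so no decision turns on the point.

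Much of this stands. The ascertainment limits are sound reasons to keep the on-treatment tables as the main ones and to label any longer-window table carefully. The lack of a decision consequence limits the importance. However, consistency between the documents does not make the tables cover the follow-up they omit. A combined-period summary that is neither named nor grouped cannot be relied on to report AESIs, and an unseen shell does not replace a statement in the SAP.

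**Conclusion.** The point holds. As specified, AESI incidence and maximum grade leave out 93 to 120 of the 150 days after PDR001 for patients who stop both drugs together or finish their last cycle. They leave out less if NIR178 continues alone, and nothing once it has run 120 days past PDR001.

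The schedule-specific figures assume the last cycle is completed, which the documents do not state. Shares of days are not shares of events. With no late-onset rate given, the number of omitted patients is unknown; the per-patient figures show only how far each one would move a rate. The data are collected and listed, so this is a reporting gap in the grouped immune-safety tables. No primary analysis or decision rule is affected. It is worth correcting because the final safety report is what remains of the study's value and the correction is small.

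**What to change.** Keep both on-treatment AESI tables. Add to SAP 2.6.2.2, in words to this effect:

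> AESI incidence and maximum CTC grade will also be tabulated, irrespective of relationship to study drug, for events that start or worsen between first dose and the later of last PDR001 dose + 150 days and last NIR178 dose + 30 days. Events starting after new antineoplastic therapy will be flagged, with a footnote that only suspected-related events are recorded from then on.

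The footnote should also note that patients who transfer to another study have no further safety follow-up.

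With this addition the untabulated window falls to zero days. The cost is a short SAP insertion and two supplementary tables, using data already collected and the existing AESI search strategy. The drawback is incomplete late ascertainment, so the added tables should supplement the on-treatment tables and not replace them.

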2.6.2.3 Deaths

Separate summaries for on-treatment and post-treatment deaths will be produced by SOC and PT.

All deaths will be listed and post-treatment deaths will be flagged. A separate listing of deaths prior to the treatment initiation will be provided for all screened patients.

Note: “Study indication” as primary reason of death should be coded using MedDRA terms based on the diagnosis eCRF field at start of study. If not coded accordingly in the database, it still must be included in the summary table. Coded reasons for deaths will then be summarized by category ‘Study indication’ and ‘Other’ (as selected by the investigator).

The death summaries cover patients from the safety set. The count of deaths reported in safety analyses may differ from that reported in the efficacy analyses.

2.6.2.4 EudraCT and clinicaltrials.gov requirements for AEs and Death summaries

For the legal requirements of clinicaltrials.gov and EudraCT, two tables (listed below) must be produced for treatment-emergent safety events (AEs/SAEs and deaths) that occurred for **150 days** after the last dose of PDR001 or 30 days after the last dose of NIR178, whichever occurred later.

1. Deaths and serious adverse events, by system organ class and preferred term.
2. Non-serious AEs regardless of study drug relationship, with an incidence rate greater than 5% by SOC and PT.

These summaries will include any events starting or worsening in the on-treatment period.

If for the same patient, several consecutive AEs (irrespective of study treatment causality, seriousness, and severity) occurred with the same SOC and PT:

- a single occurrence will be counted if there is ≤ 1 day gap between the end date of the preceding AE and the start date of the consecutive AE;
- more than one occurrence will be counted if there is > 1 day gap between the end date of the preceding AE and the start date of the consecutive AE.

The presence of at least one SAE / SAE suspected to be study drug related / non SAE has to be checked in a block e.g., among AEs in a ≤ 1 day gap block, if at least one SAE is occurring, then one occurrence is calculated for that SAE.

At the time of xml preparation, a single file per registry (i.e., 1 file for EudraCT and 1 file for CT.gov). with all reporting groups in the study will need to be submitted to the CDO.

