2.6.2.1 Adverse events (AEs)

Summary tables for adverse events (AEs) will include AEs that started or worsened during the on-treatment period, also termed as treatment-emergent AEs.

AEs will be summarized by number and percentage of patients having at least one AE, having at least one AE in each primary SOC and for each PT. AEs will be coded using the MedDRA and assessed according to the CTCAE version 4.03, respectively. The latest available MedDRA version at the time of the analyses should be used. The MedDRA and CTCAE version used should be specified in the footnote of relevant tables.

A patient with multiple occurrences of an AE will be counted only once in the respective AE category. A patient with multiple CTCAE grades for the same PT will be summarized under the maximum CTCAE grade recorded for the event. AE with missing CTCAE grade will be included in the 'All grades' column of the summary tables. In AE summaries, the primary SOC will be presented alphabetically, and the PTs will be sorted within primary SOC in descending frequency. The sort order of the PTs will be based on their frequency in the most relevant group.

Note: In AE summaries with consolidated study parts, AEs will be presented by study parts, with each part having its own sort order (see General analysis conventions under [Section 2.1](#) for detail).

The following AE summaries will be produced:

- Overview of adverse events (number and % of patients with any AE, any SAE, any fatal SAEs, any AE with dose reductions/interruptions/discontinuations, and correspondingly, with treatment-related AEs; also, AEs requiring additional therapy);
- AEs regardless of study drug relationship by SOC and/or PT, and severity;
- AEs suspected to be study drug related by SOC and/or PT, and severity;
- AEs leading to dose interruption/adjustment regardless of study drug relationship, by SOC and/or PT, and severity;

- AEs leading to dose interruption/adjustment suspected to be study drug related, by SOC and/or PT, and severity;
- AEs leading to study drug discontinuation regardless of study drug relationship by SOC and/or PT, and severity;
- AEs leading to study drug discontinuation suspected to be study drug related by SOC and/or PT, and severity;
- SAEs regardless of study drug relationship by SOC and/or PT, and severity;
- SAEs suspected to be study drug related by SOC and/or PT, and severity;

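### The registry AE and death tables are given a 150-day post-PDR001 window but described in terms that the SAP ends at 30 days, so they could omit up to 120 days of events per patient

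*SAP*

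**What the plan says.** SAP 2.6.2.4 opens with the legal requirement. Two tables "must be produced for treatment-emergent safety events (AEs/SAEs and deaths) that occurred for" a stated window: up to 150 days beyond the final PDR001 dose or 30 days beyond the final NIR178 dose, the later of the two dates applying. The first table covers deaths and SAEs by SOC and PT; the second covers non-serious AEs with incidence above 5%. Directly after that list comes the sentence "These summaries will include any events starting or worsening in the on-treatment period".

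Three definitions elsewhere in the SAP decide what this means:

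- **On-treatment period (2.1.1.5):** it runs "from date of first administration of study treatment to 30 days after date of last actual administration of study treatment". Protocol 10.5.2.1 uses the same 30-day limit.
- **Post-treatment period (2.1.1.5):** it is a separate, mutually exclusive segment "starting at day 31 after the last administration of study treatment". The extended safety follow-up is listed inside this segment: "all patients receiving PDR001 will continue to have safety evaluations for 150 days after the last dose of PDR001 or 30 days after" NIR178, if that is later.
- **Treatment-emergent (2.6.2.1):** "Summary tables for adverse events (AEs) will include AEs that started or worsened during the on-treatment period, also termed as treatment-emergent AEs".

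SAP 2.6.2 adds that all safety reporting is based on the periods in 2.1.1.5. Neither document redefines on-treatment or treatment-emergent for the registry tables.

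**The concern.** The section fixes a window of up to 150 days and then describes the content with two terms that the SAP closes at 30 days. A programmer who follows the opening sentence and one who applies the standard on-treatment flag will produce different tables, and each can point to the SAP.

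At stake is the completeness of the public safety record. Protocol 8.2.2 requires every SAE to be reported, whatever its suspected cause, until at least 150 days after PDR001 (or 30 days after NIR178 if later), and Protocol 7.1.5 and 8.1.1 set a matching window for AEs. Protocol 2.6 warns that immune-mediated events may be serious and may be more frequent with the combination. With the 30-day filter, SAEs and deaths collected after that point would be missing from the first table. The second table is affected in two ways: event counts fall, and some preferred terms could drop below the 5% cut-off and disappear.

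**Working it through.** The documents give the two windows but no figure for the difference between them, so there is no stated number to reproduce. The check is a day count.

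**Inputs**
- Registry window: later of last PDR001 + 150 days and last NIR178 + 30 days (SAP 2.6.2.4).
- On-treatment end: last study treatment + 30 days (SAP 2.1.1.5).
- Last study treatment: the last "date when a non-zero dose of either component of the treatment (NIR178 or PDR001) was administered and recorded on the DAR eCRF" (SAP 2.1.1.2), so the on-treatment clock runs from whichever drug was given last.
- PDR001 is given on day 1 of a 28-day cycle; NIR178 is taken twice daily throughout on the continuous schedule (Protocol 6.1.1).

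**Formulas.** Let day 0 be the last PDR001 dose and k the number of days by which the last NIR178 dose follows it (negative if it came earlier).
- Registry end R = max(150, k + 30)
- On-treatment end T = max(0, k) + 30
- Gap = R − T

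For k ≤ 0 the gap is 150 − 30 = 120. For k between 0 and 120 it is 150 − (k + 30) = 120 − k. For k ≥ 120 it is 0.

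| k (days) | R | T | Gap (days) |
|---|---|---|---|
| −30 | 150 | 30 | 120 |
| 0 | 150 | 30 | 120 |
| 14 | 150 | 44 | 106 |
| 27 (NIR178 to day 28 of the last PDR001 cycle) | 150 | 57 | 93 |
| 56 | 150 | 86 | 64 |
| 90 | 150 | 120 | 30 |
| 120 | 150 | 150 | 0 |
| 150 | 180 | 180 | 0 |

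As a share of the 150 days after the last PDR001 dose, the gap is at most 120/150 = 80%, and 93/150 = 62% at k = 27. A patient who never received PDR001 has no gap, because both windows then end 30 days after the last NIR178 dose.

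**The opening sentence taken alone.** It asks for treatment-emergent events over 150 days. Under 2.6.2.1 a treatment-emergent AE must start or worsen on-treatment, that is, within 30 days of the last dose. The opening sentence therefore conflicts with the SAP's definitions even without the later sentence.

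**The case against.** The strongest reply is that the later sentence says the tables include *any* on-treatment events, not *only* those. Read as a minimum, it is compatible with the 150-day requirement, which is the more specific instruction. On-treatment could also be loose shorthand for the window just stated. The filter itself will sit in the TFL shells and programming specifications (SAP Section 1), which are not part of the documents reviewed here. This much stands: the text shows that an omission could happen, not that one is planned. It does not remove the conflict, because 2.6.2.1 uses almost the same wording as the inclusion rule for the AE summary tables, and the opening sentence carries the restricted term as well.

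A second reply is that the events are reported elsewhere. All AEs are listed with post-treatment ones flagged (2.6.2.1), post-treatment deaths have their own SOC/PT summary (2.6.2.3), and selected summaries of related AEs span both periods (2.6.2). This also stands, so a reader should not infer that safety data would be lost from the study report. These outputs do not replace the registry tables, however. An unrelated SAE that starts after the on-treatment period would otherwise appear only in listings.

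A third reply is that data beyond day 30 are already limited, since only related AEs are collected once new antineoplastic therapy starts. That is correct and deserves a footnote, but it is no reason to leave out events that were collected.

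**Conclusion.** SAP 2.6.2.4 is internally inconsistent and should be corrected. Under the SAP's own definitions, the two registry tables could omit up to 120 days of events per patient: 120 when PDR001 was the last drug, 93 to 120 when NIR178 stopped within the last PDR001 cycle, and none when NIR178 continued alone for 120 days or more.

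Two stronger readings are not supported. One is that the plan definitely drops 120 days for everyone: 120 is a maximum that depends on which drug was stopped last, and the wording leaves room for a correct program. The other is that 80% of late events would be lost: 80% is the largest possible share of calendar days, and the documents give no event rate for this interval, so the number of events affected is unknown.

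The conclusion assumes that the programmers apply the definitions in 2.1.1.5 and 2.6.2.1 and that the unseen shells contain no local override. The primary endpoint and dose decisions are not affected.

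**What to change.** In SAP 2.6.2.4:

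1. Replace the reference to the on-treatment period with an explicit window: events starting or worsening from the first dose of study treatment up to the later of 150 days after the last PDR001 dose and 30 days after the last NIR178 dose.
2. Delete treatment-emergent from the opening sentence, or define it for these two tables by the same window. If only the first edit is made, 2.6.2.1 still pulls the tables back to 30 days.
3. Add a table footnote that after the start of new antineoplastic therapy only treatment-related AEs are collected.

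With the first two edits the gap is 0 days for every patient. The cost is two wording changes, one footnote and one program filter, with the shells checked to match. No new data are needed. SAP Section 1 already provides the route: an amendment before database lock or an addendum after it.
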